Priming the Brain for Rehabilitation: Brain Stimulation Followed by Constraint-Induced Movement Therapy in Adults with Severe Arm Paresis after Stroke

Study Protocol & Statistical Analysis Plan

NCT03538795

February 12, 2020

[name], Principal Investigator University of Alabama at Birmingham Birmingham, AL 35294

Priming the Brain for Rehabilitation: Brain Stimulation Followed by Constraint-Induced Movement Therapy in Adults with Severe Arm Paresis after Stroke

Outline of Study Design and Procedures

1. Overall Goals

- 1.1. Demonstrate the feasibility of combining intermittent theta burst stimulation (iTBS; a form of TMS) with an expanded form of Constraint-Induced Movement therapy (eCIMT) for treating adults after stroke with chronic, severe upper-extremity impairment.
- 1.2. Get a preliminary read on whether stimulating a brain region that controls movement of the more-affected arm with iTBS boosts the effect of eCIMT on use of the more-affected arm in everyday life and on the motor capacity of that arm.

2. Specific Aims

- 2.1. To gather preliminary data on the therapeutic effect of eCIMT plus iTBS in adults with severe, chronic hemiparesis after stroke. If the data are promising, they will be used to inform decisions about the appropriate sample size and other logistics for a RCT to be proposed to NIH that will compare the efficacy of eCIMT+iTBS to a) eCIMT alone and b) usual care.
- 2.2. To establish feasibility for using magnetic resonance spectroscopy (MRS) to identify the cellular basis of any neuroplastic changes we might observe after eCIMT+iTBS. Our labs already have expertise in magnetic resonance imaging (MRI) methods that will permit detection of changes in brain activity (fMRI) and grey matter (MRI) and white matter structures (diffusion weighted imaging; DWI). If any changes in brain activity or structure take place, MRS will permit examination of the changes in the cellular composition of those regions. As noted, grey and white matter changes have been observed after the original form of CIMT.

3. Study Design

3.1. Baseline Testing→ No treatment for 3 weeks→ Pre-treatment Testing→ eCIMT+iTBS for 3 weeks→ Post-treatment Testing→ 4-weekly follow-up phone calls→ → → 12-month follow-up.

4. Participants

- 4.1. Twenty adults more than 1-year after stroke with severe impairment of their more-affected arm, i.e., plegic or nearly plegic hands
 - 4.1.1. Grade 4 or Grade 5 with stipulation that patient can perform reliable, active extension of wrist to permit collection of fMRI data
 - 4.1.2. Participants from whom MRI would be contraindicated will be excluded
 - 4.1.2.1. This covers all of the exclusion criteria for the iTBS procedure but one, which is exclusion of any candidates with a history of seizures.

5. Intervention

- 5.1. eCIMT: Expanded CIMT (eCIMT) combines CIMT with neurodevelopmental techniques (NDT) for managing tone.
- 5.2. iTBS: Intermittent theta burst stimulation is a form of excitatory transcranial magnetic stimulation (TMS) that involves delivery of magnetic pulses in bursts and at a frequency that mimics the frequency of theta brain waves. It has robust evidence of promoting long-term potentiation, whereas more standard forms of TMS do not.
 - 5.2.1. Initial stimulation threshold determined with FDI muscle in less-affected hand

- 5.2.2. Hotspot for stimulation of cortical area controlling movement of more-affected hand/wrist identified with support of fMRI images obtained during movement of more-affected wrist.
- 5.3. Treatment period: 15 consecutive weekdays
- 5.4. Treatment setting: iTBS in Sparks Rm 405, eCIMT in Taub Therapy Clinic.
 - 5.4.1.Participant will be transported from Taub Therapy Clinic to iTBS facility and back using wheel chair.
- 5.5. Typical Treatment Day (4-4.5 hours):
 - 5.5.1. eCIMT- Transfer Package component (structured interview on arm use, review of daily diary, problem-solving, etc...; 15-20 min typically but substantially longer on first day)
 - 5.5.2. iTBS (20-40 minutes on first treatment day, 10-15 minutes thereafter)
 - 5.5.3. eCIMT- NDT, i.e., facilitation/tone management component: stretching, weight-bearing, oscillation, icing, vibration (60 minutes)
 - 5.5.4. iTBS (10-15 minutes)
 - 5.5.5. eCIMT- shaping component, i.e., training on tasks with frequent, positive feedback and raising of the bar for reward in progressive, small increments; simulated ADL practice (60 minutes)
 - 5.5.6.iTBS (10-15 minutes)
 - 5.5.7.eCIMT- shaping component, i.e., training on tasks with frequent, positive feedback and raising of the bar for reward in progressive, small increments; simulated ADL practice (60 minutes)eCIMT- Transfer Package component (structured interview on arm use, review of daily diary, problem-solving, etc...; 15-20 min typically but substantially longer on first day)
 - 5.5.8.eCIMT- Transfer Package component (assignment of home skill assignment, etc...; 5-10 min typically but substantially longer on first day)
 - 5.5.9. eCIMT- padded safety mitt will be worn on less-affected to discourage its use both during treatment and at home. Time that mitt is worn will be determined by safety considerations and the degree to which the patient needs to use the less-affected arm to accomplish tasks that are typically bilateral.
 - 5.5.10. eCIMT- splinting and orthotic devices will introduced during eCIMT sessions on an as needed basis to support use of the more-affected arm to complete tasks.

6. Motor Function Testing

- 6.1. Occasions: Baseline, Pre-treatment, Post-treatment, 12-month follow-up
- 6.2. Setting: Taub Therapy Clinic and Blinded Testing Room ("Pink Room," SRC R056). Grade 4/5 WMFT will be conducted in Pink Room to permit collection of kinematic data.
- 6.3. Tests
 - 6.3.1. Grade 4/5 Motor Activity Log (everyday use of more-affected arm)
 - 6.3.2. Canadian Occupational Performance Measure (everyday use of arms)
 - 6.3.3. Grade 4/5 Wolf Motor Function Test (motor capacity of that arm)

7. Data Analysis

- 7.1. Primary outcome is change from baseline to post-treatment on MAL
- 7.2. If the enrollment target is met, a repeated measures ANOVA will be used to evaluate whether statistically significant improvement is present on the primary outcome. The repeated measures factor will be Testing Occasion (baseline, pre-treatment, post-treatment, 12-month follow-up). If the omnibus test is significant, specific contrast statements will be used to test when improvement takes place.

- 7.3. Parallel methods will be used to evaluate the secondary outcomes.
- 7.4. If the sample size is substantially smaller than projected, changes on the primary outcome will be characterized using descriptive statistics.

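### The primary MAL change runs from Baseline, so any change in the 3 untreated lead-in weeks counts in full as part of the primary effect

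*Combined protocol and SAP*

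**What the plan says.** Section 3.1 gives the sequence as "Baseline Testing→ No treatment for 3 weeks→ Pre-treatment Testing→ eCIMT+iTBS for 3 weeks→ Post-treatment Testing", with follow-up to 12 months. There is one group. Section 6.1 lists four separate test points: "Occasions: Baseline, Pre-treatment, Post-treatment, 12-month follow-up". Section 7.2 uses the same four as levels of the repeated measures factor. The word baseline in 7.1 therefore means the first test, not the one taken just before treatment.

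Section 7.1 then sets the endpoint: "Primary outcome is change from baseline to post-treatment on MAL". If enrollment meets its target, 7.2 applies a repeated measures ANOVA and adds: "If the omnibus test is significant, specific contrast statements will be used to test when improvement takes place". Section 7.3 carries the same approach to the secondary outcomes. Section 7.4 covers a shortfall: "If the sample size is substantially smaller than projected, changes on the primary outcome will be characterized using descriptive statistics".

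**The concern.** The design includes an untreated period with a test at each end, which is the only within-person comparison available in a single-arm study. The primary outcome does not use it that way. It adds the untreated weeks to the treated weeks and reports the sum. Change over the lead-in could come from repeat testing, regression to the mean or real change in arm use, and all of it would be read as response to eCIMT+iTBS.

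Aim 2.1 seeks preliminary data on the therapeutic effect and says promising data will inform the sample size and logistics of a later RCT. The headline figure taken forward should therefore describe the treated weeks.

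**Working it through.** **Inputs.** From the plan: four occasions (6.1, 7.2), 3 untreated then 3 treated weeks (3.1), one group of 20 (3.1, 4.1). The plan states no alpha, SD, correlation, effect size or lead-in change, so it has no figure to reproduce. Assumed here: two-sided 0.05, compound symmetry with correlation 0.6, and a lead-in shift d, in SDs of the change score, that persists at later visits.

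**Identity.** Let L = Pre − Baseline and T = Post − Pre. Then Post − Baseline = L + T. With assumed values T = 0.5 and L = +0.3 the primary measure gives 0.8; with L = −0.3 it gives 0.2. Post − Pre gives 0.5 in both cases.

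**No treatment effect.** The occasion means are (0, d, d, d), with mean 0.75d and sum of squared deviations 0.75d². The change-score SD is σ√(2(1−ρ)), so the omnibus noncentrality is 20 × 0.75 × 2 × d² = 30d² on 3 and 57 df, and the correlation drops out. At d = 0.3 this is 2.7, and the noncentral F gives 23.5% rejection. An ungated paired baseline-to-post t test has noncentrality d√20 = 1.34 on 19 df and rejects 24.7% of the time. Simulation (100,000 runs per row; gated means tested only after a significant omnibus test) gives:

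| d | Omnibus | Baseline-to-post, gated | Pre-to-post, gated | Pre-to-post, ungated |
|---|---|---|---|---|
| 0 | 5.0% | 1.8% | 1.8% | 5.0% |
| 0.1 | 6.7% | 2.9% | 1.9% | 4.9% |
| 0.2 | 12.4% | 6.9% | 2.5% | 4.9% |
| 0.3 | 23.9% | 15.4% | 3.2% | 5.0% |
| 0.5 | 59.1% | 46.7% | 4.6% | 5.1% |

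At correlation 0.8 and d = 0.3 the omnibus rate is 23.7% and the gated baseline-to-post rate 15.3%, as the algebra predicts. A Greenhouse-Geisser correction lowers the omnibus rate at d = 0.3 to 21.2%.

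**Lead-in fall.** Take a true pre-to-post effect of 0.5 SD, half kept at 12 months, and d = −0.2. The means are (0, −0.2, 0.3, 0.05). Over 40,000 runs, improvement is detected as follows:

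| Contrast | Gated | Ungated |
|---|---|---|
| Baseline-to-post | 19% | 25% |
| Pre-to-post | 39% | about 56% |

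With no lead-in change, the gate alone lowers pre-to-post power from 56% to 45%.

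**Descriptive fallback (7.4).** With a true effect of 0.5 SD, the lead-in share of the described change is d/(d + 0.5): 0.1/0.6 = 17%, 0.2/0.7 = 29%, 0.3/0.8 = 38%, 0.5/1.0 = 50%.

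**Precision of the alternative.** Under compound symmetry both changes have variance 2σ²(1−ρ), so nothing is lost. If correlation decays as AR(1) over the two equal 3-week intervals, Var(Post − Baseline) = 2σ²(1−ρ²) and Var(Post − Pre) = 2σ²(1−ρ). At ρ = 0.6 the SD ratio is √1.6 = 1.26, in favor of pre-to-post.

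**The case against.** The strongest reply is that 7.2 largely handles this. The ANOVA includes the Pre-treatment test, and contrasts meant to locate the timing of improvement would naturally include pre-to-post. If they do, the gated pre-to-post contrast stays between 1.8% and 4.6% in the table, so lead-in change would not produce an excess of false claims about the treated weeks. The omnibus rejections are also not errors of that test, because the occasion means do differ and the test makes no claim about timing. Both points are right. They show that the data can separate the periods; they do not change what 7.1 defines as the primary result. The contrasts are unnamed and conditional, and 7.4 calls for no separate segments, although it does not forbid them.

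Other points also carry weight:

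- Participants are more than 1 year after stroke, so the lead-in change may be small. At zero the two measures have the same expected value.
- The loss of power depends on the effect size. With an assumed 1.0 SD effect, half kept at 12 months, and a −0.2 SD shift, gated power is 92% from Baseline and 98% from Pre-treatment.
- Comparing 19% with 56% mixes the starting point with the gate. The starting point alone accounts for 19% against 39% gated, or 25% against 56% ungated.
- The planned RCT compares arms, where lead-in change common to the arms cancels, and neither starting point estimates what iTBS adds to eCIMT. The pilot figure still bears on whether the data look promising.
- Other contrasts are defensible. Post minus the mean of the two earlier tests has 25% less variance under compound symmetry but keeps half of any lead-in change. (Post − Pre) − (Pre − Baseline) uses the lead-in as a control but has 3 times the variance of Post − Pre.

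**Conclusion.** The concern holds. That lead-in change enters the primary measure with coefficient 1 follows from 3.1, 6.1 and 7.1 alone and needs no outside figure. How large the distortion would be is unknown. For assumed persisting rises of 0.1 to 0.5 SD and no treatment effect, the gated baseline-to-post contrast rejects about 3% to 47% of the time. Under the descriptive fallback, the same rises would make up 17% to 50% of the reported change if the true effect were 0.5 SD. These figures rest on n = 20, two-sided 0.05, equal variances and correlations and, for the rejection rates, a shift that lasts to 12 months.

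This should be fixed. It is not fatal, because the Pre-treatment MAL is collected and the treated weeks can be isolated. As written, the primary outcome does not isolate them.

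**What to change.** - **7.1:** define the primary outcome as the MAL change between the Pre-treatment and Post-treatment tests.
- **7.2:** name pre-to-post as the primary contrast and test it without requiring a significant omnibus result. Report the Baseline to Pre-treatment change with its 95% CI beside it, labeled as the untreated-period change. Removing the gate is a separate gain from moving the starting point and can be justified on its own.
- **7.3:** use the same starting point for the secondary outcomes.
- **7.4:** state that both segments will be described if the sample falls short.
- **Limits to state:** the change removes only the lead-in component. Retest and expectation effects within the treatment weeks remain, and iTBS is still not separated from eCIMT.

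The cost is a few sentences, with no new visits, tests or patients. No precision is lost under equal variances and correlations, and some is gained if correlation decays with time.

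### The baseline-to-post-treatment primary outcome is tested through a four-occasion ANOVA, with no rule for participants who have no 12-month score

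*Combined protocol and SAP*

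**What the plan says.** Section 7.1: "Primary outcome is change from baseline to post-treatment on MAL". This uses two scores per person.

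Section 7.2 gives the test and its trigger: "If the enrollment target is met, a repeated measures ANOVA will be used to evaluate whether statistically significant improvement is present". It then sets the factor: "The repeated measures factor will be Testing Occasion (baseline, pre-treatment, post-treatment, 12-month follow-up". Contrasts that locate the improvement follow only if the omnibus test is significant, and none is named in advance.

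Section 7.4 gives the fallback: "If the sample size is substantially smaller than projected, changes on the primary outcome will be characterized using descriptive statistics". It puts no number on the shortfall and does not say whether enrolled or analysable participants are counted.

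The target is in Section 4.1: "Twenty adults more than 1-year after stroke with severe impairment of their more-affected arm". The schedule in Section 6.1 matches the four-level factor: "Occasions: Baseline, Pre-treatment, Post-treatment, 12-month follow-up". Section 3.1 shows three untreated weeks between baseline and pre-treatment, and phone calls between post-treatment and the 12-month visit.

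The documents state no analysis population, missing-data rule, expected 12-month loss, alpha, effect size or SD.

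**The concern.** The outcome and its test use different data. Someone with both MAL scores that define the primary outcome, but no 12-month score, has nothing missing from that outcome. A classical repeated measures ANOVA works on complete rows and would drop that person from the test.

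The omnibus gate adds a second dependence on the later visit. Whether the primary comparison is tested at all turns on a result across four occasions, including the amount of gain still present at 12 months.

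The trigger counts enrolment, which is settled before anyone knows how many will have four scores. If Section 7.4 also counts enrolment, 20 enrolled with 14 seen at 12 months are tested, while 15 enrolled and fully observed might only be described.

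At stake are power and precision and, if return is related to response, bias. Section 2.1 intends the data to "inform decisions about the appropriate sample size and other logistics for a RCT". A one-arm change does not estimate a between-group difference, but its mean and SD are among the figures a planner would take from this study.

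**Working it through.** **Inputs from the documents:** target 20 (4.1); two-occasion outcome (7.1); four-occasion factor, enrolment trigger and omnibus gate (7.2).

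**Assumptions:** two-sided alpha 0.05; change of 0.8 SD (SD of the individual baseline-to-post changes); all 20 have both MAL scores; 12-month loss of 20% or 30%, so 20 × 0.8 = 16 or 20 × 0.7 = 14 completers. The target of 20 has no stated derivation, so there is no figure to reproduce.

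**Step 1: does meeting enrolment secure 20 complete rows?** With independent loss at rate d, the chance that all 20 return is (1 − d)^20. This is 0.95^20 = 36%, 0.90^20 = 12% and 0.80^20 = 1.2%. It does not.

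**Step 2: power from loss alone.** For the paired t-test, power is taken from the noncentral t distribution with n − 1 df and noncentrality 0.8√n.

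**Step 3: power with the omnibus gate added.** Simulation in n completers: compound symmetry with r = 0.5, no change before treatment, and the gain kept, halved or lost by 12 months. The rule is Greenhouse-Geisser omnibus p < 0.05, then paired baseline-to-post contrast p < 0.05. The range is over the three 12-month patterns.

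| n | Paired test | Omnibus, then contrast |
|---|---|---|
| 20 | 92% | 89–92% |
| 16 | 85% | 78–83% |
| 14 | 79% | 70–77% |

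The gate costs up to about 3 points with no loss, and more as completers fall.

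**Step 4: precision.** The 95% CI half-width, in SDs of change, is t(0.975, n − 1)/√n with a contrast-specific error. With the pooled ANOVA error under sphericity it is t(0.975, 3(n − 1))/√n.

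| n | Contrast-specific | Pooled |
|---|---|---|
| 20 | 2.093/√20 = 0.468 | 2.002/√20 = 0.448 |
| 16 | 2.131/√16 = 0.533 | 2.014/√16 = 0.503 |
| 14 | 2.160/√14 = 0.577 | 2.023/√14 = 0.541 |

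Against 0.468, the paired interval in all 20, the completer interval is 8% (pooled) to 14% wider at n = 16, and 16% to 23% wider at n = 14.

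**Step 5: bias.** Take change as N(0, 1) in SD units and the probability of return as logistic in change, with the intercept set to give the stated return rate. The completer mean exceeds the true mean by:

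| Odds of return per SD of change | 20% loss | 30% loss |
|---|---|---|
| × 1 | 0 | 0 |
| × 2 | 0.13 SD | 0.19 SD |
| × 3 | 0.19 SD | 0.27 SD |

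The sign reverses if poorer responders return more.

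**The case against.** A reader might infer that the plan limits the primary test to 12-month completers. The documents do not say so. Section 7.2 names a repeated measures ANOVA but no estimator or analysis set. A mixed-model version would keep partial data, and a later contrast could be run on everyone with both scores. This stands: what the text shows is silence, with complete-case exclusion as the usual behaviour of the named method. The omnibus gate remains under any of these readings.

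A reader might also infer that 20 enrolled with 14 seen at 12 months would certainly be tested. Section 7.4 refers to sample size, which can mean analysable participants, and 14 might then only be described. This stands too; the defect is an undefined count and threshold.

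Nor do the documents limit the reported mean and SD of change to completers, so it cannot be said that the planning figures for the RCT will be distorted. Section 7.2 governs a significance test.

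Finally, this is a one-group pilot seeking feasibility and a first indication of effect (1.1, 1.2), and with high retention the loss is minor. That limits the weight of the point but does not justify tying a two-occasion outcome to a third and fourth occasion.

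**Conclusion.** The point holds as a mismatch plus an omission. The primary outcome uses two occasions, its test uses four and sits behind an omnibus gate, and nothing says what happens to a participant without a 12-month score. The enrolment trigger does not protect the analysable number.

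The size is conditional. With full retention, loss costs nothing and the gate little. With 14 of 20 returning, a complete-case analysis and a true change of 0.8 SD, power falls from 92% to 79% through loss, and to about 70–77% with the gate. These two causes should be kept apart: the whole drop should not be put down to missing 12-month visits. The gated figures use a contrast-specific error and compound symmetry; other error structures would shift them. The bias figures need return to depend on response, for which the documents give no evidence either way.

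**What to change.** In Section 7.2, make the primary test the paired baseline-to-post-treatment comparison in all participants with both MAL scores, whether or not they are seen at 12 months, and without the omnibus gate. Report the number analysed, mean change, SD and 95% CI at any sample size.

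Keep the four-occasion analysis as supporting evidence on when improvement occurs. Run each contrast in everyone who has the scores it uses, or fit a likelihood-based mixed model to all available scores. The contrast over the untreated weeks (baseline to pre-treatment) then does not depend on the 12-month visit either.

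Base the switch between Sections 7.2 and 7.4 on the number of participants with the scores the analysis needs, at a threshold the sponsor states in advance.

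The cost is a few sentences in Section 7, with no new data, visits or participants and no change to Section 7.1. There are two downsides. Analyses may rest on different numbers of participants, which must be stated. With full retention and sphericity, the paired interval is slightly wider than the pooled ANOVA interval (0.468 against 0.448 SD).

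### The primary outcome is a baseline-to-post-treatment MAL change (7.1), but 7.2 judges it by a four-occasion omnibus F and reaches any contrast, none of them named, only if that F is significant.

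*Combined protocol and SAP*

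**What the plan says.** - **7.1** fixes the outcome: "Primary outcome is change from baseline to post-treatment on MAL". That is one difference between two visits.
- **7.2** applies if the enrollment target is met. It says "a repeated measures ANOVA will be used to evaluate whether statistically significant improvement is present on the primary outcome". It goes on to list four visits for this model: "The repeated measures factor will be Testing Occasion (baseline, pre-treatment, post-treatment, 12-month follow-up". Follow-up tests are conditional: "If the omnibus test is significant, specific contrast statements will be used to test when improvement takes place". No contrast is listed.
- **7.3** extends this to the other measures: "Parallel methods will be used to evaluate the secondary outcomes".
- **7.4** is the alternative route, with no gate: "If the sample size is substantially smaller than projected, changes on the primary outcome will be characterized using descriptive statistics".
- **1.2 and 2.1** give the purpose. The study is to "Get a preliminary read on whether stimulating a brain region that controls movement of the more-affected arm" boosts the effect of eCIMT, and "If the data are promising, they will be used to inform decisions about the appropriate sample size" of a later RCT.

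**The concern.** The outcome has one degree of freedom and a direction. The test assigned to it has three degrees of freedom and no direction, and it responds to a difference at any of the four visits, including pre-treatment and 12 months. Two things follow from the text as written.

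1. A significant F is not evidence that MAL improved from baseline to post-treatment. It could reflect only a decline by 12 months.
2. A non-significant F stops the sequence before any contrast, so the change defined in 7.1 never receives its test. Noise at the 12-month visit can cause this, although that visit plays no part in the 7.1 definition.

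What is at stake is not a confirmatory claim. Planning the RCT in 2.1 needs the estimate of the 7.1 change and its precision. Section 7.2 does not require either to be reported when F is not significant.

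**Working it through.** **Inputs.** From the documents: n = 20 (4.1) and four occasions (7.2), so F has 3 and 3 × 19 = 57 df. There is no stated power figure to reproduce. Assumed: alpha 0.05, two-sided paired contrast, SD 1 at each visit and, unless stated otherwise, equal true means at baseline and pre-treatment. Section 7.2 mentions no sphericity correction, so simulated results are given as uncorrected / Greenhouse-Geisser (GG).

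**Step 1: direct test.** The paired t has 19 df and noncentrality dz × √20, where dz is the mean change divided by the SD of change. Power is 0.40, 0.57, 0.72, 0.80 and 0.92 at dz = 0.4, 0.5, 0.6, 0.66 and 0.8.

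**Step 2: omnibus F and gate, equal correlations.** λ = n × Σ(μⱼ − μ̄)² / (SD_change² / 2) = 40 × dz² × c, where c is the sum of squared deviations of the four means in units of the change d. At dz = 0.66, 40 × 0.4356 = 17.42. Gated power is the share of 40,000 simulated trials in which both F and the contrast are significant.

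| Means (baseline, pre, post, 12 months) | c | λ | Power of F | Direct contrast | Gated |
|---|---|---|---|---|---|
| 0, 0, d, d (gain kept) | 1 | 17.42 | 0.94 | 0.80 | 0.79 |
| 0, 0, d, d/2 (half kept) | 0.6875 | 11.98 | 0.81 | 0.80 | 0.73 |
| 0, 0, d, 0 (gain lost) | 0.75 | 13.07 | 0.85 | 0.80 | 0.75 |
| 0, d/2, d, d/2 (lead-in drift) | 0.5 | 8.71 | 0.66 | 0.80 | 0.65 |

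Across common correlations of 0.6, 0.8 and 0.9, the first three profiles lose 1.4–6.7 points uncorrected and 1.9–8.5 with GG. Drift during the untreated lead-in raises the loss to about 15 points.

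**Step 3: 12-month scores less correlated with the earlier visits.** The error mean square pools all four occasions, so a noisier 12-month visit weakens F but not the paired contrast. Direct power is again held at 0.80, with a raw change of 0.66 × √(2(1 − r)), where r is the correlation among the first three visits. Gated power, uncorrected / GG:

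| r, first three / with 12 months | Raw change | Gain kept | Half kept | Gain lost |
|---|---|---|---|---|
| 0.8 / 0.6 | 0.42 SD | 0.69 / 0.65 | 0.60 / 0.53 | 0.62 / 0.56 |
| 0.85 / 0.6 | 0.36 SD | 0.61 / 0.53 | 0.51 / 0.41 | 0.54 / 0.44 |
| 0.85 / 0.5 | 0.36 SD | 0.54 / 0.44 | 0.43 / 0.31 | 0.46 / 0.34 |
| 0.9 / 0.6 | 0.30 SD | 0.47 / 0.35 | 0.37 / 0.24 | 0.39 / 0.27 |
| 0.9 / 0.5 | 0.30 SD | 0.39 / 0.27 | 0.29 / 0.17 | 0.32 / 0.20 |

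These are not a lower bound. Lead-in drift in the 0.9 / 0.5 pattern gives about 0.22 (GG 0.12–0.13).

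**Step 4: larger effects.** With no lead-in drift, at a raw change of 0.5 SD the largest loss is 10 / 12 points under equal correlations and 16 / 29 in the less-correlated patterns. At 0.8 SD it is 1.0 / 1.4 points.

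**Step 5: no baseline-to-post change, 0.5 SD fall at 12 months only.** F is significant in 68–100% / 59–100% of trials across the eight correlation patterns. This is not a false-benefit rate. If the baseline-to-post contrast is then run, it falsely shows improvement in about 2% of all trials, or roughly 2.5–3.5% of those with a significant F.

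**Step 6: missing 12-month visits.** The plan does not say how they are handled. If the ANOVA used complete cases and 4 of 20 lacked that visit (an assumption), F would rest on 16 participants. Its power at dz = 0.66 would be 0.86, 0.70, 0.74 and 0.55 for the four profiles in Step 2. The paired contrast could still use all 20 (0.80).

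**The case against.** An omnibus F followed by contrasts is a conventional analysis, and 7.2 gives it a purpose: to find out when improvement occurs. That question needs all four visits. Any sensible set of contrasts would include post-treatment against an earlier visit, and the sponsor very probably intends this. Once that contrast is run, false improvement is rare (Step 5). Section 2.1 speaks of promising data, not significant data, and nothing in 7.2 forbids reporting the mean change. The large losses need a small change and particular correlations. When the gain is kept and correlations are equal, F is the more sensitive test: 94% against 80%. The issue also disappears if 7.4 applies.

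Most of this stands, and it limits the weight of the point. It does not remove it. Probable intent does not name the contrast, and it does not lift the gate. The planned contrast step answers the first consequence but not the second, because it is not reached when F is not significant. The sensitivity of F concerns whether anything changed at any visit, which is not the question in 7.1.

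**Conclusion.** The concern holds. The mismatch between 7.1 and 7.2 is plain from the text, and nothing elsewhere in the document repairs it. It applies whenever 7.2 applies, and through 7.3 to the secondary outcomes.

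The cost in power is less certain. It is modest under equal correlations with no lead-in change, can be large when the true change is small and 12-month scores are less correlated with the rest, and is negligible at 0.8 SD when there is no lead-in change. All of these figures rest on the assumptions listed, since the documents supply only the sample size and the number of occasions. In a preliminary single-group study this is a change that should be made, not one that invalidates the design.

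**What to change.** Reword 7.2 along these lines: the primary outcome is tested by the single pre-specified baseline-to-post-treatment MAL contrast (paired t-test or model contrast); its estimate and 95% CI are reported whatever the omnibus F shows; the four-occasion ANOVA and the other contrasts are supportive analyses of when change occurs. State the alpha as well. Two-sided 0.05 is the assumption used here and is not in the documents. In 7.3, add that each secondary outcome's baseline-to-post-treatment contrast is likewise estimated with a 95% CI regardless of F.

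Baseline-to-post-treatment spans the three untreated weeks in 3.1. If the sponsor would rather test pre- to post-treatment, 7.1 should be amended to match.

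The cost is wording only, with no new data, visits or multiplicity scheme. The omnibus F loses its lead role, and with it a more sensitive signal that some change occurred when the gain is fully kept and correlations are equal (94%, GG 93%, where the direct contrast has 80%). The other contrasts remain unadjusted and must be read as supportive.

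### Section 7 names no comparison of the treated 3-week change with the untreated 3-week change, although section 3.1 provides the data for it

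*Combined protocol and SAP*

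**What the plan says.** Section 3.1 sets out a one-group sequence: "Baseline Testing→ No treatment for 3 weeks→ Pre-treatment Testing→ eCIMT+iTBS for 3 weeks→ Post-treatment Testing". Follow-up calls and a 12-month visit come after it. Section 4.1 plans for "Twenty adults more than 1-year after stroke with severe impairment of their more-affected arm".

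Section 7.1 reads: "Primary outcome is change from baseline to post-treatment on MAL". That change starts before the untreated weeks and ends after the treated ones.

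In section 7.2, provided that recruitment reaches its planned number, the intention is that "a repeated measures ANOVA will be used to evaluate whether statistically significant improvement is present on the primary outcome". The levels are given as follows: "The repeated measures factor will be Testing Occasion (baseline, pre-treatment, post-treatment, 12-month follow-up". Further tests depend on a significant overall result, and of these the plan says only that "specific contrast statements will be used to test when improvement takes place". The section gives no occasions, weights, null value or rule of interpretation for these contrasts.

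Section 7.3 applies the same methods to the secondary outcomes. Section 7.4 falls back on descriptive statistics if the sample is substantially smaller than planned. Neither mentions a comparison of treated with untreated change.

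**The concern.** With no concurrent group, a gain over the treated weeks can be separated from drift, practice or repeated-rating effects only by setting it against the gain over the untreated weeks. Section 3.1 provides for this: "No treatment for 3 weeks" is followed by "eCIMT+iTBS for 3 weeks". The analysis section does not say that the comparison will be made.

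Two consequences follow. First, the primary change in 7.1 carries any drift from both intervals. Second, contrasts that ask when improvement occurs lend themselves to separate tests of each interval. A significant treated change next to a non-significant untreated one does not show that the two changes differ, and at this sample size a non-significant untreated change does not show that drift is absent.

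Section 2.1 says that promising data will inform the sample size of a later randomised trial against eCIMT alone and usual care. A change that includes drift would overstate the gain to be expected over such comparators.

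**Working it through.** **No figure to reproduce.** The documents give no significance level, standard deviation, drift or effect size, and no justification for the sample size.

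**Inputs.** From the documents: 20 participants (4.1); four occasions, with an untreated and then a treated interval of 3 weeks each (3.1, 7.2); contrasts gated by the omnibus test (7.2). Assumed: two-sided 0.05, counting only the improvement direction; complete data; the same drift m in both intervals, in SDs of the 3-week change; no change after post-treatment.

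**What each contrast estimates.** With treatment effect τ:
- Post − Baseline (the 7.1 outcome): 2m + τ
- Post − Pre: m + τ
- (Post − Pre) − (Pre − Baseline): τ

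Only the third is free of equal drift.

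**Chance of a significant improvement when τ = 0, ungated.** This uses a noncentral t with 19 df, critical value 2.093 and noncentrality (mean/SD of the contrast) × √20. Under equal correlations at m = 0.3, the noncentrality is 0.3 × 4.472 = 1.34 for Post − Pre, giving 25%, and 0.6 × 4.472 = 2.68 for Post − Baseline, giving 72%. At m = 0.2 / 0.3 / 0.5:
- Post − Pre: 13% / 25% / 56%
- Post − Baseline: 40% / 72% / 99%
- Direct contrast: 2.5% throughout

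At m = 0 all three are at 2.5%.

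**Chance that Pre-to-Post is significant and Baseline-to-Pre is not, when τ = 0, after the omnibus gate (simulation).** In the second pattern the correlations are 0.9 for adjacent early visits, 0.8 for baseline with post-treatment, and 0.5 for any visit with 12 months.

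| Drift m (SD) | Equal correlations | Falling to 0.5 at 12 months |
|---|---|---|
| 0 | 1% | 1% or less |
| 0.1 | 3% | 1% |
| 0.2 | 10% | 3% |
| 0.3 | 21% | 7% |
| 0.4 | 30% | 12% |
| 0.5 | 31% | 16% |

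The direct contrast, ungated, falsely shows improvement in about 2.5% in every row.

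**Precision cost.** Under equal correlation ρ:
- Var(Post − Pre) = 2(1 − ρ)σ²
- Var(Post − 2·Pre + Baseline) = 6σ² + 2ρσ²(−2 + 1 − 2) = 6(1 − ρ)σ²

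The ratio is 3, so the SE is √3 = 1.73 times as large. Under the second pattern the variances are 0.2σ² and 6σ² + 2σ²(−1.8 + 0.8 − 1.8) = 0.4σ², so the SE ratio is √2 = 1.41.

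Power of the direct contrast under equal correlations: at τ = 1.0 SD the noncentrality is 1.0/1.732 × 4.472 = 2.58, giving 69%; at 1.2 SD it is 3.10, giving 84%. The effect detectable with 80% power is 0.66 SD for Post − Pre against zero. For the direct contrast it is 0.66 × 1.732 = 1.14 SD under equal correlations, or 0.66 × 1.414 = 0.93 SD where the ratio is √2.

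**The case against.** A reader might infer that 7.2 tests each interval against zero, rules out a test of the difference, and will conclude that treatment worked when only the treated interval is significant. The documents do not say this. The contrasts are left open, and weights of +1, −2, +1 form a legitimate contrast on the same Testing Occasion factor. No rule of interpretation is written. The fallacy of comparing significance levels is a risk in how results may be read, not a step in the plan.

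The size of the risk also depends on a drift that the documents do not give. Participants are more than a year after stroke, so large natural recovery in 3 weeks cannot be presumed. At zero drift there is no excess, and at 0.1 SD the gated figure is 3% or less. A test of the untreated interval would itself give some information on drift. The study is a feasibility pilot seeking a preliminary indication, and the direct contrast is less precise.

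All of this stands, and it limits how firmly the point can be put. It does not remove the gap. Whatever contrasts are intended, none is named that compares the two changes, and leaving the choice open lets it be made after the data are seen. Retest and rating effects remain possible in chronic stroke. The observation that the 7.1 change includes the untreated weeks needs no inference about unspecified contrasts.

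**Conclusion.** The concern holds in this form: the plan collects a matched untreated interval but names no analysis that uses it as the control for the treated one, and its primary change spans both. If 7.2 is carried out as interval-by-interval tests and both intervals share the same drift, the misleading pattern occurs after the omnibus gate in anything from about 1% of trials at zero drift to 31% (equal correlations) or 16% (correlation falling at 12 months) at 0.5 SD. These figures illustrate a risk under assumed drift; they are not error rates of the plan as written. For an uncontrolled pilot this is a worthwhile, inexpensive improvement rather than a flaw that invalidates the study.

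**What to change.** Add to 7.2 one pre-specified contrast, run whatever the omnibus result: (Post-treatment − Pre-treatment) − (Pre-treatment − Baseline), that is, weights +1, −2, +1 on Post, Pre and Baseline, reported as an estimate with its 95% CI. Base any statement that improvement exceeded that of the untreated weeks on this contrast. Keep reporting the separate interval changes. Under 7.3, use the same contrast for the secondary outcomes; under 7.4, report the same difference descriptively.

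The cost is a sentence or two in the SAP and one contrast on data already planned. The downsides should be stated with it: the lower precision shown above, the assumption that drift is similar in the two intervals, and the fact that the contrast cannot separate iTBS from eCIMT.
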